9.5 Study Size

According to the US Department of Transportation data through 2021 (US DOT [WWW]), approximately 3% of licenced drivers in the US have motor vehicle crashes during a year; therefore, approximately 3% of participants are expected to have an accident during the 12 months follow-up. This incidence rate is restricted to crashes involving either the car insurance or the police and might be slightly different than the incidence of MVAs self-reported by drivers.

Due to the lack of clear evidence for elevated incidence of MVAs in individuals with migraine compared to the general population, it is assumed that the incidence of MVAs in the general population can be expected in any of the comparison groups (3% per year). A sample of 793 participants per treatment group would provide 80% power at 5% level of significance for detection of a hazard ratio (HR) of 2.0. Given this is a safety study, no alpha correction method will be used. In order to achieve this sample size, an additional 20% will be targeted for enrolment in anticipation of participant dropout (992 per treatment group). A HR of 3.0 could be detected with a minimum of 397 participant after attrition, assuming an MVA rate of 3% in the lower risk group. Thus, a number of 1000 participants per treatment group, is targeted to be enrolled into the study. Due to a limited source population of lasmiditan-treated patients, challenges are anticipated for the recruitment of participants in the Lasmiditan Group.

If a sufficient number of participants treated with lasmiditan is enrolled, prospective follow-up and a comparative analysis will be executed as part of the final analysis (See Section 9.7.2.2).

If the required sample size is not achieved in the Lasmiditan Group and/or the number of incident MVA in the study period is insufficient to provide meaningful comparison between Lasmiditan Group and comparator groups (Other Acute Medication Group and No Acute Medication Group), unadjusted incidence rates of MVAs in each treatment group with precision estimates will be provided as primary analysis (see Section 9.7.2.2.2.2) and descriptive statistics will summarise participants characteristics, treatment patterns, driving patterns and self-reported MVAs experience through the 12-months of follow-up period.

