The crude (unadjusted) estimates of the number of incident MVAs, total person-time, and incidence rate of first occurrence of MVA since study enrolment under each treatment strategy will be presented. These figures will be calculated using the person-time-trial level analytic data set described in Section 9.7.2.2.2.1.

A marginal structural pooled logistic regression model will be fit to the data structure described in Section 9.7.2.2.2.1 to estimate the relative hazard of MVA between the Lasmiditan Group and the Other Acute Medication Group, as well as between the Lasmiditan Group and the No Acute Medication Group. Using the notation in Section 9.7.2.2.2.1, the model will take on the following form:

$$logit[pr(D_{m+k+1} = 1 | A_k, L_0, \overline{D}_{m+k} = 0, \overline{C}_{m+k+1} = 0)] = \beta_{0,m+k} + \beta_1^T A_k + \beta_2^T L_0$$

where $\beta_{0,m+k}$ is a time-varying intercept (i.e., a parametric estimation of the baseline hazard) that will include a spline or other polynomial function of follow-up interval 'k' and trial number 'm'; β_1 is a vector of the log hazard ratios of interest (comparing a reference treatment strategy to the remaining strategies); β_2 is a vector of coefficients of the baseline covariates. Under the rare disease assumption, the exponentiated β_1 coefficients will approximate a hazard ratio, provided the event rate within each 'k' time interval is <8%. This will be verified at the time of the analysis.

To adjust for potential confounding, stabilised time-varying inverse probability of treatment to weights will be estimated as follows:

$$SW_{m+t}^{A} = \prod_{k=m}^{m+t} \frac{f(A_{k}|\bar{A}_{k-1}, L_{0}, \bar{D}_{k-1} = 0)}{f(A_{k}|\bar{A}_{k-1}, L_{0}, \bar{L}_{k-1}, \bar{D}_{k-1} = 0)}$$

LY573144 Lasmiditan

Non-Interventional Protocol

Given that there are three comparator treatment strategies, the density in the numerator and denominator of this stabilised weights will be estimated using a multinomial regression model. Informally, the numerator of the weight is the probability of receiving the treatment that the participant actually received at time 'k,' conditional on treatment and baseline covariate histories and the denominator of the weight is the probability of receiving the treatment that the participant actually received at time 'k,' conditional on treatment, baseline covariate, and time-varying covariate histories.

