Because participants are censored when they deviate from their assigned treatment strategies, selection bias may result. To account for this, inverse probability of censoring weights will be estimated as follows:

$$SW_{m+t}^{C} = \prod_{k=m}^{m+t} \frac{f(C_{k+1} = 0 | \bar{A}_k, \bar{C}_k = 0)}{f(C_{k+1} = 0 | \bar{A}_k, L_0, \bar{L}_k, \bar{C}_k = 0)}$$

The density in the numerator and denominator of this weight will be estimated using a logistic regression model. Informally, the numerator of the weight is the probability of being uncensored in the next interval conditional on treatment history and the denominator of the weight is the probability of being uncensored in the next interval conditional on treatment, baseline covariate, and time-varying covariate histories.

Observations in the marginal structural pooled logistic model specified above will be weighted by the joint density of the two weights as follows:

$$SW_{m+t}^{A,C} = SW_{m+t}^A \times SW_{m+t}^C$$

Observations in this analysis are not independent due to the use of weighting and allowance of repeated entry into the analytic cohort (i.e., through participation in more than one nested trial). To account for this lack of independence, nonparametric bootstrap will be used to estimate standard errors and confidence intervals.

A weighted and unweighted table of baseline characteristics will be generated using the persontime-trial level data set described in Section 9.7.2.2.2.1. Absolute standardised mean differences (ASMD) will be used to evaluate imbalances in these characteristics between participants assigned to the lasmiditan treatment strategy vs. the remaining two treatment strategies. ASMDs of the <0.1 will be considered imbalanced.

Contingencies:

1. The joint density of the inverse probability weights $SW_{m+t}^{A,C}$ may contain extreme values if there are few patients in the study sample that possess a particular combination of characteristics within each level of treatment strategy and time interval. If this occurs, weights will be incrementally truncated at upper and lower P^{th} percentile (e.g., 99.9th, 99.8th, 99.7th percentiles, etc.) until there are no longer extreme weights.

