- 2. It may not be possible to achieve balance between all potential confounders across treatment groups (i.e., ASMD<0.1). Imbalances in baseline characteristics will be addressed with a re-specification of inverse probability weights (e.g., Changing the functional form of the variable or including interaction terms). However, if imbalances remain these will be described along with their potential impact on the outcome estimate(s).
- 3. It may not be possible to model all collected covariates due to sparsity, collinearity, or other factors that can preclude convergence of statistical models. For this reason, the final variables and functional forms of the baseline (L_0) and time-varying (\overline{L}_k) covariate vectors described in the models above will be determined at the time of analysis.
- 4. The time interval of the analysis, denoted 'k', directly influences the dimensionality of the dataset, and concequent computational intensity of the analysis. Particularly, choosing a time interval of one day will greatly increase the number of rows in the analytic data set and, concequently, increase the computation time of nonparametric bootstrap algorithms for standard error estimation. Therefore, if computation times are too great then the time interval of the analysis may be expanded accordingly (e.g., to one week or one month).

9.7.2.2.2.3 Missing Data

Missing data may arise from participants who skip a single survey only, or who are lost to followup (defined as non-responce on two concecutive follow-up surveys). Participants who are lost to follow-up will be censored at 67 days following the opening of their last survey (as participants are allotted 7 days to answer each 30-day survey). Missing data arising from non-response will be addressed using *last observation carried forward*, where the most recent survey responses are "carried forward" under the assumption that participants' treatment and confounder histories did not change during the time spanning from the participant's final response through the period of non-response.

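### The censoring-weight numerator omits the baseline covariates that the outcome model and the treatment-weight numerator both use, which costs precision but does not bias the hazard ratio

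*Protocol*

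**What the plan says.** All of this is in Protocol Section 9.7.2.2.2.2, including its list of contingencies.

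- **Outcome model.** The pooled logistic model contains treatment, a function of follow-up interval and trial number, and L0; β2 "is a vector of coefficients of the baseline covariates". It has no treatment-by-L0 term.
- **Treatment weight.** The numerator is the probability of the treatment received, "conditional on treatment and baseline covariate histories".
- **Censoring weight.** Its reason is given as "Because participants are censored when they deviate from their assigned treatment strategies, selection bias may result". In words, "the numerator of the weight is the probability of being uncensored in the next interval conditional on treatment history"; the denominator is the probability of "being uncensored in the next interval conditional on treatment, baseline covariate, and time-varying covariate histories". The printed formula agrees with the words: L0 is in the denominator only.
- **Extreme weights.** Contingency 1 says the joint "weights will be incrementally truncated at upper and lower" percentiles until none is extreme.
- **What stays open.** Contingency 3 says the final variables and forms of the L0 and time-varying "covariate vectors described in the models above will be determined at the time of analysis". That leaves open what L0 contains, not which numerator conditions on it.

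**The concern.** A stabilised-weight numerator may condition on whatever the outcome model conditions on. L0 is in the outcome model, and the plan uses this freedom for the treatment weight but not for the censoring weight. The ratio SW^C then reflects both the time-varying selection it is needed for and all the censoring predicted by baseline values, multiplied over 12 monthly intervals or more if the interval is shorter.

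The two weights also do closely related work. Treatment is constant within a nested trial and deviation is censored, so both largely model staying on strategy. One is stabilised on L0 and the other is not.

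At stake is the precision of a comparison with few events: 3% of 1000 is about 30 accidents in a comparator group. A few large weights on event rows can widen the bootstrap interval. They can also trigger truncation, which trims the wanted time-varying correction together with the avoidable part.

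**Working it through.** **1. The plan's own figure.** Section 9.5 claims "80% power at 5% level of significance for detection of a hazard ratio (HR) of 2.0" with 793 per group. Inputs: 3% comparator risk, HR 2.0, two-sided 5% (assumed two-sided). Freedman events: (1.960 + 0.842)² × [(1 + 2)/(1 − 2)]² = 70.64. Lasmiditan risk: 1 − 0.97² = 0.0591. So n = 70.64/(0.03 + 0.0591) = 792.8, or 793; with dropout 793/0.8 = 991.25, or 992. Both reproduce. The calculation contains no allowance for weighting.

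**2. The two numerators compared.**
- Printed: SW^C = ∏ f(C=0 | Ā) / f(C=0 | Ā, L0, L̄).
- With L0: SW^C = ∏ f(C=0 | Ā, L0) / f(C=0 | Ā, L0, L̄).

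If censoring depends on L0 only, the second weight is exactly 1, while the first still varies between people.

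**3. Simulated loss of precision.** Two groups of 793, 12 intervals, 3% comparator risk, HR 2.0, one standard-normal L0 score. The monthly censoring rate and the L0 log-odds per SD are assumptions. The plan gives only 20% dropout; 2% a month is 1 − 0.98¹² = 21.5% over the year if everyone has the same rate. Entries are var(log HR) with the printed numerator divided by var(log HR) with L0 added. Set-up A: about 1500 replicates, censoring driven by L0 only. Set-ups B and C: 500 and 400 replicates, fitted weights and a time-varying covariate.

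| Monthly censoring | L0 log-odds per SD | A | B | C |
|---|---|---|---|---|
| 2% | 0.5 | 1.01 | 1.01 | 1.01 |
| 5% | 0.5 | 1.06 | 1.03 | 1.07 |
| 10% | 0.5 | 1.13 | 1.10 | 1.20 |
| 5% | 1.0 | 1.30 | 1.22 | 1.41 |
| 10% | 1.0 | 1.55 | 1.53 | 1.63 |

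A further run by total censoring (200 replicates, fitted weights, L0 log-odds 0 to 1.0) gave these ratios of standard errors:
- About 20% censored: 1.00-1.04, a variance ratio of at most 1.04² = 1.08.
- 31-39% censored: 1.00-1.16, at most about 1.34.
- 53-58% censored, log-odds up to 0.5 only: 1.00-1.10, at most 1.21. The two strongest L0 settings at this level failed to fit and are not reported.

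Mean HR was 1.94-2.11 under both numerators, so no bias was seen.

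**4. Weights and truncation.** At 31-39% censoring the average largest weight was 1.8-27 with the printed numerator and 1.3-1.7 with L0 added. In set-up B at 10% a month and log-odds 1.0, the SD of the log HR was 0.456 as printed, 0.402 after capping at the 1st and 99th percentiles, and 0.369 with L0 added. Power is Φ(ln 2/SD − 1.96), giving 33%, 41% and 47%. Capping recovers only part of the loss.

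**5. What the change could cost.** Large-sample values use the assumptions of set-up A (log-hazard 0.3 per SD of L0) plus an assumed treatment-by-L0 interaction of 0.3. Without censoring the fitted HR is 2.29. The printed numerator gives 2.29 at both 5% and 10% a month (log-odds 1.0). The variance saved is taken from the SDs of set-up A, which has no interaction.

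| Setting | HR with L0 added | Squared log shift from 2.29 | Variance saved |
|---|---|---|---|
| 5%, 0.5 | 2.18 | 0.049² = 0.0024 | 0.308² − 0.300² = 0.0049 |
| 5%, 1.0 | 2.10 | 0.087² = 0.0075 | 0.351² − 0.308² = 0.0283 |
| 10%, 1.0 | 2.01 | 0.130² = 0.0170 | 0.457² − 0.368² = 0.0734 |

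The squared shift is smaller than the variance saved in each row.

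**The case against.** The strongest case for the plan is that the printed weight is valid. Its formula and text agree, the two numerators need not match, and weighting back to the uncensored population protects against a misspecified L0 model. That is correct, and it limits the point in three ways.

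- **A reader might infer that the HR is biased.** It is not: with correct models the printed estimator is consistent.
- **A reader might infer that adding L0 never changes the target.** That holds only if the additive L0 model is adequate. Under effect modification the HR shifts towards the effect in those who remain uncensored (step 5). With an omitted quadratic term of 0.15 and L0-dependent censoring in the lasmiditan group only, the HR was 2.00 as printed, against 1.93 and 1.91 with L0 added at 5% and 10% a month. In the settings examined these shifts run towards the null, which matters in a safety study. Contingency 3 itself expects that sparsity may limit the model.
- **A reader might infer a loss of more than ten power points.** Set-up A gives 11 and 14 points, but only at 5-10% monthly censoring with log-odds 1.0 per SD and no truncation; with capping at the 99th percentile it is about 4-6 points. The documents state neither input. The simulations also use two groups and a single entry, not three groups with re-entry.

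The objection that the matter is already left open does not stand. Contingency 3 leaves open the contents and forms of the vectors. Contingency 2 allows re-specification of weights when baseline imbalance is found. Neither puts L0 in this numerator.

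**Conclusion.** The mismatch is real and is fixed in both formula and text. It is a minor efficiency point, not an error of validity. At the only attrition figure the plan gives, 20% dropout, the variance cost is about 1% with a moderate L0 effect, which is negligible. It grows if deviation from strategy adds much censoring. That is plausible for drugs taken as needed, with groups defined by use in the prior 30 days (Section 9.1), but no deviation rate is stated. Under assumed monthly censoring of 5-10%, the variance rises by about 5-20% with a moderate L0 effect, and by about 20-60% only with a strong one. The change also has a small downside, since it leans on the additive L0 model, as the treatment weights already do. In the settings examined the precision gained outweighed the shift.

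**What to change.** Condition the SW^C numerator on treatment history and L0: SW^C = ∏ f(C_{k+1}=0 | Ā_k, L0, C̄_k=0) / f(C_{k+1}=0 | Ā_k, L0, L̄_k, C̄_k=0). Use the same L0 vector and functional form as in the outcome model and the treatment-weight numerator, and change the informal description to match. Report the HR with the printed numerator as a sensitivity analysis, so that any shift from effect modification or misspecification of L0 is visible.

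The cost is one more covariate vector in a logistic model, one corrected sentence and one additional fit. No new data are needed.

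### The ASMD balance rule is stated backwards, and the weighted baseline table judges treatment weights that, with L0 in their numerator, leave baseline imbalance as observed

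*Protocol*

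**What the plan says.** All of this is in Protocol Section 9.7.2.2.2.2 (Statistical Models) and the contingencies that close it.

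- **Balance rule.** Weighted and unweighted baseline tables are produced, lasmiditan against each of the other two strategies. The rule reads: "ASMDs of the <0.1 will be considered imbalanced".
- **Contingency 2.** It opens: "It may not be possible to achieve balance between all potential confounders across treatment groups (i.e., ASMD<0.1" (the parenthesis closes there). It continues: "Imbalances in baseline characteristics will be addressed with a re-specification of inverse probability weights", giving functional form and interaction terms as examples. Imbalance that remains is to be described with its possible effect on the estimate.
- **Treatment weight.** The numerator is the probability of the treatment received, "conditional on treatment and baseline covariate histories and the denominator of the weight" being defined next; the denominator is "conditional on treatment, baseline covariate, and time-varying covariate histories". The displayed formula agrees: L0 is in both, and the time-varying history is in the denominator only.
- **Censoring weight.** Here "the numerator of the weight is the probability of being uncensored in the next interval conditional on treatment history"; L0 enters the denominator only.
- **Outcome model.** The pooled logistic model contains L0, and its beta_2 "is a vector of coefficients of the baseline covariates".

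**The concern.** There are two separate faults.

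The first is a contradiction. One sentence calls small differences imbalanced; a few lines later small differences define balance. Taken literally, the first sentence would flag well-matched covariates and pass badly matched ones.

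The second remains once the direction is corrected. The baseline table is meant to show whether weighting has dealt with baseline differences, and the stated response to a failure is to rework the weights. But these weights are built to remove the association of treatment with time-varying history given L0, not its association with L0. Real baseline differences would stay above 0.1, reworking the weights would not clear them, and the report would describe remaining imbalance that the outcome regression has already addressed. The same table could not reveal a badly specified L0 term in the outcome model, which is where baseline confounding is actually handled. This is the only covariate-balance check the protocol specifies for its non-randomised comparison.

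**Working it through.** The 0.1 cut-off is a rule, so there is no figure to reproduce.

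**1. The two statements side by side**

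| ASMD | Balance-rule sentence | Contingency 2 |
|---|---|---|
| below 0.1 | imbalanced | balanced |
| 0.1 or above | not flagged | not balanced |

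They cannot both stand. Contingency 2 carries the action, and it shows the intended direction.

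**2. What the treatment weight does to L0.** Take one interval and suppress treatment history. The weight is f(A|L0) / f(A|L0,L). Averaging over L given L0:

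sum over L of f(L|L0) × f(A|L0,L) × f(A|L0)/f(A|L0,L) = f(A|L0)

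The weighted law of treatment given L0 is the observed one, so the L0 means by arm, and hence the ASMD, do not move. If L adds nothing beyond L0, the weight is 1. With f(A) as numerator the same sum gives f(A), so treatment no longer depends on L0. In the product over intervals, the argument applies factor by factor, given treatment history.

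**3. What the censoring weight does.** Its form is f(C=0|A) / f(C=0|A,L0,L). Among the uncensored it restores each arm's own baseline mix. It does not make the arms alike.

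**4. Simulation.** All inputs are assumptions: n = 60,000; three arms by multinomial logit; one baseline covariate L0; one earlier time-varying covariate L (0.5 × L0 plus noise). The L0 log-odds slope for the second arm is 0.2, 0.4 or 0.6, and 1.5 times that for the third (lasmiditan-like) arm. Cells give the ASMD of L0 for the lasmiditan-like arm against the reference arm / the other arm.

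| Weighting | slope 0.2 | slope 0.4 | slope 0.6 |
|---|---|---|---|
| None | 0.560 / 0.191 | 0.801 / 0.255 | 1.026 / 0.349 |
| Planned treatment weight | 0.561 / 0.192 | 0.807 / 0.257 | 1.026 / 0.349 |
| Re-specified (quadratic, cubic, interaction terms) | 0.560 / 0.192 | 0.805 / 0.257 | 1.028 / 0.351 |
| Planned treatment × censoring weight, uncensored only | 0.575 / 0.198 | 0.824 / 0.265 | 1.041 / 0.355 |
| Treatment weight, numerator without L0 | 0.002 / 0.001 | 0.002 / 0.007 | 0.005 / 0.005 |

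With the censoring weight added to the last row, the range is 0.001 to 0.013.

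The planned weight does act on L: against the reference arm its ASMD falls from 0.756, 0.865 and 0.906 to 0.255, 0.371 and 0.448. The remainder runs through L's correlation with L0, so a check on time-varying covariates has to be made conditional on L0.

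**5. Effect estimate under a true null** (outcome depends on L0 and L only; lasmiditan-like arm against reference; range over the three slopes)

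| Analysis | Odds ratio |
|---|---|
| Crude | 1.76 to 2.23 |
| Planned weight, L0 not in outcome model | 1.43 to 1.85 |
| Planned weight, L0 in outcome model (as planned) | 0.99 to 1.02 |

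**6. Price of a marginal numerator in the effect-estimating weights.** The denominator conditions on prior treatment; f(A) alone does not. Assume three equal groups and switchers split evenly.

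- 80% persistence: stayers weigh (1/3)/0.8 = 0.417 and switchers (1/3)/0.1 = 3.33. The mean weight is 1 and the mean square is 0.8 × 0.174 + 0.2 × 11.11 = 2.36. Effective sample size is 1/2.36, about 42%.
- 90% persistence: weights are 0.370 and 6.67, the mean square is 4.57, and effective sample size is about 22%.

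**The case against.** The strongest reply has four parts.

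- **The reversal is a drafting slip.** The sentence is visibly garbled and Contingency 2, where action is taken, has the right direction. This stands as to intent: it is unlikely that analysts would apply the rule literally. The sentence is still wrong and needs correcting.
- **L0 in the numerator is a standard stabilised form, valid when L0 is also in the outcome model, as here.** This stands in full. A reader might infer that baseline confounding is uncontrolled or the hazard ratio biased. The protocol does not support that: the beta_2 term adjusts for L0, and the null result in step 5 agrees.
- **Contingency 2 offers its remedies only as examples, and Contingency 3 leaves final covariates and forms open.** This also stands. A reader might infer that no re-specification could ever balance L0. That goes too far, because dropping L0 from the numerator would do it. The point holds while L0 stays there, and for the remedies actually named.
- **Describing the remaining imbalance leaves room to say that L0 is adjusted by regression.** It does, but the protocol does not say so, and it sends the analyst to the weights first.

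The scope is also conditional. Under Sections 9.5 and 9.7.2.2, unadjusted incidence rates become the primary analysis if the Lasmiditan Group is too small (Section 9.5 adds too few accidents), and the weights then play no part.

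**Conclusion.** Both faults hold, in limited form. The balance threshold is reversed in one sentence and contradicted by Contingency 2. The weighted baseline table, read with either direction, cannot show whether baseline confounding is controlled, and the named remedies cannot clear what it flags. In the simulation the planned treatment weight moved L0 ASMDs by at most 0.006, and the joint weight left them at 0.198 to 1.041 among the uncensored. The sizes are assumed; the lack of movement is algebraic and needs only that L0 stays in the numerator and that the weight models are reasonably specified.

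What is affected is the diagnostic and the response to it. No bias in the hazard ratio is shown, provided L0 is adequately specified in the outcome model. That proviso matters: for a covariate in the numerator, the weights give no protection if its outcome term is omitted (1.43 to 1.85 under a true null in step 5).

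**What to change.** 1. In the balance-rule sentence, state that an ASMD of 0.1 or more counts as imbalanced.
2. Keep the L0-conditional stabilised weights for the effect estimate. State that L0 is adjusted in the outcome model, and redirect Contingency 2 so that baseline imbalance prompts a review of how L0 is specified in that model rather than of the weights.
3. Use the weighted ASMD check for the time-varying covariates, conditional on L0 and treatment history. If a weighted balance table for L0 is wanted, compute it on one time-zero row per participant-trial, with a diagnostic-only version of the weights whose numerator omits L0. If that numerator keeps prior treatment, read balance within levels of prior treatment. Such a table checks the treatment model, not the form of the outcome regression.

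The cost is a few lines of wording and a little more analysis work. Putting a marginal f(A_m) into the effect-estimating weights is not recommended as a cheap alternative: it drops prior treatment as well as L0, and if treatment is persistent the weights could become much more variable (working, step 6).
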